### **Analysis Sets**

#### **Intention-To-Treat (ITT) Population**

The ITT population includes all participants who received at least one dose of study drug and will be analysed and presented by the on-treatment monitoring arm assigned at randomisation.

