## 4.0 Study design

### 4.1 Summary of study design

This study will be conducted as a Phase IIIb, randomised, controlled, multicentre, international trial.

There will be a maximum screening period of 6 weeks prior to Baseline. Eligible patients will be randomised into one of two on-treatment monitoring strategies; standard clinical trial monitoring (4-weekly on-treatment visits) vs simplified monitoring (no on-treatment visits) (see Figure 1). Randomisation will be 1:2 (standard vs simplified) and all participants will receive treatment with glecaprevir (300mg)/pibrentasvir (120mg) for 8 weeks.

All participants will attend the clinic for screening and baseline visit. Randomisation will occur at the baseline visit.

The two on-treatment monitoring strategies will differ as follows:

- **Standard monitoring arm participants** will have on-treatment clinic visits at weeks 4 and 8 (EoT).
- **Simplified monitoring arm participants** will have no on-treatment clinic visits.

Study nurse phone contact will also be made to participants in BOTH arms 1-2 days prior Week 4 and EoT (Week 8) visits to provide standardized reporting of adverse events, concomitant medication and adherence.

One post treatment clinic visit will be conducted at SVR12 (week 20) for all participants.

[figure not shown]

Figure 1: Study schema

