## **5.0 Treatment of participants**

Participants will receive eight week of open-label glecaprevir (300mg)/pibrentasvir (120mg) in an oral once-daily fixed dose. Dose modifications are prohibited.

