## **10.0 Statistics**

### **10.1 Sample Size**

The study is designed to enrol a total of 375 patients: 125 in the standard arm and 250 in the simplified arm. The primary efficacy endpoint of SVR12 will be assessed within each arm, and the primary comparison of SVR12 rates will be for non-inferiority of standard to simplified arms. With these patient numbers, the study has approximately 80% power to show non-inferiority to standard treatment monitoring with a lower confidence bound for the difference (standard – simplified) in SVR12 rates greater than –6% (assuming an SVR12 rate of 96% in both arms).

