### **10.5 Definition of Intent-to-treat Population**

Intent-to-treat (ITT) and modified intent-to-treat (mITT) populations will be used for efficacy analyses. All patients who receive at least one dose of study drug will be included in the ITT population (and safety population). The mITT population will exclude patients who have completed treatment (>95% adherence) (according to phone contact at week 8), but have not returned for their SVR12 assessment. The data from the ITT and mITT will be presented by the treatment arm assigned at the time of randomisation. For the primary analyses of non-inferiority tests, the percentage of patients achieving SVR12 in each arm will be calculated with confidence intervals (CI) using the normal approximation to the binomial distribution.

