**Safety Population**

The Safety population includes all participants who received at least one dose of study drug and will be analysed and presented according to the actual on-treatment monitoring arm received during the study.

The ITT population will be used for primary efficacy analyses, and the safety population will be used for all safety analyses.

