**Table 1. Recruitment and follow-up**

Participant disposition	Total N (%)	Standard N (%)	Simplified N (%)
Total participants screened, n		NA	NA
Participants screened and excluded, n		NA	NA
Participants allocated to treatment (randomised), N			
Commenced allocated treatment, n/N (%)			
Did not commence allocated treatment, n/N (%)			
Treated Participants			
Completed allocated treatment course, n (%)			
Discontinued treatment, n (%)			
Lost to study follow-up, n (%)			
Study follow up			
Completed study follow up, n (%)			
Did not complete study follow up, n (%)			
Population for analysis			
Intention-to-treat, n			
Modified intention-to-treat, n			
Modified intention-to-treat virological-failure, n			
Per protocol, n			

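### The primary set labelled ITT is a treated set, and no all-randomised analysis is planned; the conclusion is exposed only if non-starters are imbalanced between arms

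*SAP*

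**What the plan says.** The SAP (Analysis Sets) states: "The ITT population includes all participants who received at least one dose of study drug". Participants are grouped by randomised arm. Protocol 10.5 matches: "All patients who receive at least one dose of study drug will be included in the ITT population (and safety population". The SAP then says that "The ITT population will be used for primary efficacy analyses". The hypothesis in protocol 2.1 is also stated for the ITT population.

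The other efficacy sets (mITT, mITT-VF and per-protocol) do not restore undosed participants. They add further conditions on adherence, outcome or attendance. Neither document plans an analysis of everyone randomised.

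Treatment is open-label (protocol 5.0). On timing, protocol 4.1 says "Randomisation will occur at the baseline visit", and protocol 6.1 lists dispensing in both arms at that same visit. SAP Table 1 has a row by arm for "Did not commence allocated treatment, n/N". The SAP's missing-data section counts missing primary-endpoint data as failure, and its Study Definitions class loss to follow-up and a missing week 12 HCV RNA as non-virologic failure.

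**The concern.** Taking a dose happens after randomisation, and by then participant and site both know the arm. A set conditioned on that event is no longer protected by randomisation. What is randomised here is the monitoring strategy, and both arms receive the same drug. Starting treatment and staying in care are therefore part of what an all-randomised comparison would capture.

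The SAP's safeguard for incomplete data is missing equals failure, but it works only inside the analysis set. Someone classed as never dosed is neither a success nor a failure.

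There is also a gap in the rules. The SAP (Definition of Study Day) says how to estimate an unknown last-dose date. It does not say how to classify a participant who was dispensed drug and then lost, with no information on whether a first dose was taken. That decision sets the denominator and would be made with the arm known.

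At stake is whether the reported non-inferiority result describes all randomised participants, and whether a reader could check that it does.

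**Working it through.** **Inputs.** Sample size: "125 in the standard arm and 250 in the simplified arm" (protocol 10.1). Response: "assuming an SVR12 rate of 96% in both arms" (same section). Margin: -6 points, simplified minus standard (SAP, Statistical Methods). Decision: lower limit of a 95% CI (protocol 10.3), by the normal approximation to the binomial. The number of non-starters is not in the documents, so 0 to 5 in one arm is an assumed range.

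**1. The plan's own power.**
SE = sqrt(0.96×0.04/125 + 0.96×0.04/250) = 0.02147.
Power = Φ(0.06/0.02147 − 1.96) = Φ(0.835) = 79.8%.
This reproduces the stated figure of about 80%. The sample size is not in question.

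**2. Room before the margin.**
Lower limit = (p_simp − p_std) − 1.96 × sqrt[p_simp(1−p_simp)/n_simp + p_std(1−p_std)/n_std].
With no non-starters (240/250 vs 120/125) it is 0 − 1.96×2.147 = -4.21 points. Holding the standard arm at 120/125, 13 simplified-arm failures still pass (237/250: -5.60) and 14 do not (236/250: -6.06). Ten failures are expected at 96%.

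**3. Non-starters in the simplified arm only** (96% SVR12 among those dosed, rounded to whole participants; standard arm 120/125):

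| Non-starters | Dosed set | Lower limit | All randomised | Lower limit |
|---|---|---|---|---|
| 1 | 239/249 | -4.23 | 239/250 | -4.67 |
| 2 | 238/248 | -4.25 | 238/250 | -5.14 |
| 3 | 237/247 | -4.27 | 237/250 | -5.60 |
| 4 | 236/246 | -4.29 | 236/250 | -6.06 |
| 5 | 235/245 | -4.32 | 235/250 | -6.52 |

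Four is on the edge. Without rounding (0.96×246 = 236.16 successes) the all-randomised limit is -5.99.

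**4. How often the two sets would disagree.** Enumerating all outcomes at 96% among those dosed, with every non-starter in the simplified arm, the dosed set passes and the all-randomised set fails with probability 6.9% for one non-starter, 14.6% for two, 23.8% for three and 33.4% for four.

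**5. Relaxing the imbalance.** Keep the four simplified-arm non-starters and add some in the standard arm, all randomised:
- One (236/250 vs 119/125): -0.8 − 1.96×2.402 = -5.51.
- Two (236/250 vs 118/125): 0 − 1.96×2.519 = -4.94.

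With non-starters split 1:2, it takes about 6 standard plus 12 simplified before the expected limit crosses (-6.02).

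**6. Non-starters in the standard arm only.** With one, the dosed set (240/250 vs 119/124) gives -4.20 and the all-randomised set (240/250 vs 119/125) gives 0.8 − 1.96×2.279 = -3.67. The all-randomised set is then the easier one to pass.

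**7. Power of an all-randomised primary analysis.** With a balanced non-start rate r, q = 0.96(1−r), SE = sqrt[q(1−q)(1/125 + 1/250)] and power = Φ(0.06/SE − 1.96):
- r = 0.5%: SE 0.02266, power 75.4%.
- r = 1%: SE 0.02378, power 71.3%.
- r = 2%: SE 0.02585, power 64.1%.

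**The case against.** The strongest case against is that this hardly matters in practice. Randomisation and dispensing share a visit, the drug is the same, and scheduled monitoring first differs around week 4. Nurses call both arms at weeks 4 and 8 with an adherence survey and up to three attempts (protocol 6.1). Standard-arm participants keep their drug until the SVR12 visit so that accountability is comparable across arms (protocol 5.2). Protocol and SAP define the set identically and openly, and Table 1 already discloses non-starters by arm. All of this stands, and it argues that non-starters will be few.

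It also disposes of several stronger inferences:
- *That participants start unobserved at home.* Neither document says where the first dose is taken.
- *That the simplified arm can shed early losses as undosed while the standard arm cannot.* The standard arm's extra clinic visits reveal nothing about someone lost straight after baseline. SAP Table 11 counts loss to follow-up as an ITT failure, and Table 1 separates it from not starting. No rule reclassifies losses as undosed.
- *That the plan expects non-starters.* An empty disposition row provides for them but does not predict any.
- *That a few exclusions, wherever they fall, decide the result.* If not starting is unrelated to arm, four non-starters all fall in the larger arm with probability (2/3)^4 = 16/81, about 20%. One or two in the standard arm restore non-inferiority.

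The definition itself is not rescued. Being rare and disclosed does not put undosed participants into any planned efficacy analysis, and the case of an unknown first dose still has no rule.

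**Conclusion.** The point holds as a gap in the definition of the primary set. The set called ITT is conditional on dosing, undosed participants are outside missing equals failure, and no planned analysis includes them.

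The effect on the conclusion depends on imbalance. Under the design assumptions, four non-starters confined to the simplified arm (1.6% of 250) move the lower limit from -4.29 to -6.06, just past the margin. Fewer would do so only if the observed result were already closer to -6. Non-starters split in proportion to allocation need to number about 18, and non-starters in the standard arm alone act in the opposite direction.

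A reader might infer that the definition is biased towards non-inferiority. The documents do not support that: they give neither a non-start rate nor evidence that it would differ by arm. The figures rest on 96% SVR12 among those dosed, full recruitment of 125 and 250, and an assumed range of non-starters. The change is worth making because it costs little and removes a choice that would otherwise be made with the arm known.

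**What to change.** 1. Analyse all randomised participants by assigned arm, counting anyone without a post-treatment week 12 HCV RNA as a failure. Preferably make this the primary ITT analysis. At minimum, pre-specify it as a sensitivity analysis reported beside the primary result.
2. Rename the dosed set treated or modified ITT, using a label distinct from the existing mITT set, and keep a dosed set for safety.
3. State that a participant who was dispensed drug and then lost, with the first dose unknown, stays in the efficacy set as a failure.

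Table 1 already reports non-starters by arm, so no new table is needed for that.

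**Cost.** If everyone starts, no result changes. If some do not, SVR12 falls slightly and so does power: from about 80% to about 75% at a balanced 0.5% non-start rate and 71% at 1%. Replacing the primary set needs a protocol amendment with ethics approval (protocol 13.0). The sensitivity-analysis route leaves the protocol's primary set as it is and could be written into the SAP.

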#### **Modified Intention-To-Treat (mITT) Population**

The mITT population excludes participants who have completed treatment (>95% adherence) (according to phone contact at week 8), but have not attended follow up at post-treatment week 12.

**Modified Intention-To-Treat Virologic Failure (mITT-VF) Population**

The mITT population includes participants in the ITT population with SVR12 or virologic failure, but excludes participants with non-virologic failure or reinfection.

**Per-Protocol Population**

The per-protocol population includes all participants who completed the 8-week regimen of glecaprevir/pibrentasvir (with >95% adherence, according to phone contact at week 8) and attended follow up at post-treatment week 12.

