### 3.3 Exclusion criteria

Participants who meet any of the exclusion criteria are not to be enrolled in this study.

- 1) History of any of the following:
  - a. Clinically significant illness (other than HCV) or any other major medical disorder that may interfere with the participant treatment, assessment or compliance with the protocol; participants currently under evaluation for a potentially clinically significant illness (other than HCV) are also excluded.
  - b. Clinical hepatic decompensation (i.e. ascites, encephalopathy or variceal haemorrhage).
  - c. Solid organ transplant.
  - d. History of severe, life-threatening or other significant sensitivity to any excipients of the study drugs.
- 2) Any of the following lab parameters at screening:
  - a. ALT > 10 x ULN
  - b. AST > 10 x ULN
  - c. Direct bilirubin > ULN
  - d. Platelets < 90,000/ $\mu$ L (cells/mm^3) if Fibroscan® <12.5 kPa OR < 150,000/ $\mu$ L (cells/mm^3) if Fibroscan® is unavailable and patient is included with APRI <1
  - e. Creatinine clearance (CLcr) < 50 mL/min
  - f. Haemoglobin < 12g/dL for males; <11g/dL for females
  - g. Albumin < LLN
  - h. INR > 1.5 ULN unless subject has known haemophilia or is stable on an anticoagulant regimen affecting INR
- 3) Pregnant or breastfeeding female.
- 4) HBV infection (HBsAg positive).
- 5) Use of prohibited concomitant medications as described in section 5.3.
- 6) Chronic use of systemically administered immunosuppressive agents (e.g. prednisone equivalent > 10 mg/day for >2 weeks).
- 7) Therapy with any anti-neoplastic or immunomodulatory treatment (including supraphysiologic doses of steroids and radiation)  $\leq$  6 months prior to the first dose of study drug.
- 8) Any investigational drug  $\leq$  6 weeks prior to the first dose of study drug.
- 9) Ongoing severe psychiatric disease as judged by the treating physician.

- 10) Positive result of a urine drug screen at the Screening Visit for opiates, barbiturates, amphetamines, cocaine, benzodiazepines, phencyclidine, propoxyphene, or alcohol, with the exception of a positive result (including methadone) associated with documented short-term use or chronic stable use of a prescribed medication in that class.
- 11) Injecting drug use within the previous six months.
- 12) Inability or unwillingness to provide informed consent or abide by the requirements of the study.

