### **Protocol violations/exemptions**

Number, proportion, type and reason for any protocol violations will be described (Table 5). For this purpose, a protocol violation/exemption will be defined as any person who was enrolled in the study despite failing an inclusion criterion and/or meeting an exclusion criterion.

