**Table 5. Protocol violations or deviations**

Protocol violations or deviations	Reason	N (%)
Total number with protocol violations or deviations		
Violation of study inclusion or exclusion criteria		
Enrolment errors		

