## STUDY ENDPOINTS

**Table 9. Study endpoints and outcomes**

Primary endpoint	Non-inferiority of simplified on-treatment monitoring to standard on-treatment monitoring (ITT population)	Included in primary analysis
Secondary endpoints	Non-inferiority of simplified on-treatment monitoring to standard on-treatment monitoring (mITT population)	Included in primary analysis
	Non-inferiority of simplified on-treatment monitoring to standard on-treatment monitoring (per-protocol population)	Included in primary analysis
	Virologic failure	Included in primary analysis
	On-treatment adherence	Included in primary analysis
	Early treatment discontinuation	Included in primary analysis
	SVR12, by genotype	Included in primary analysis
	SVR12, by HIV serostatus	Included in primary analysis
	Adverse events	Included in primary analysis
	Laboratory abnormalities	Included in primary analysis
	Unscheduled clinic visits	Included in primary analysis
	Change from baseline in patient reported outcome summary measures	Included in primary analysis
	Presence of baseline polymorphisms	Included in primary analysis
	Presence of treatment-emergent substitutions in patients with virologic failure	Included in primary analysis
Additional pre-specified outcomes	Cost-effectiveness	Not included in primary analysis
	Health practitioner acceptability	Included in primary analysis

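### The SAP's per-protocol set has no eligibility condition, so the secondary per-protocol non-inferiority comparison can include people outside the trial's target population; the likely effect is small

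*SAP*

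**What the plan says.** The SAP, under Analysis Sets, admits to the per-protocol set everyone who met two conditions. The first is treatment: "The per-protocol population includes all participants who completed the 8-week regimen of glecaprevir/pibrentasvir", with adherence above 95% by the week 8 phone contact. The second is attendance: "and attended follow up at post-treatment week 12". Nothing else is required.

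Under Protocol violations/exemptions, the SAP defines a violation or exemption as "any person who was enrolled in the study despite failing an inclusion criterion and/or meeting an exclusion criterion". The only planned use is description in Table 5, which has a row for "Violation of study inclusion or exclusion criteria" and no columns by arm. No section links Table 5 to an analysis set.

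The protocol is explicit about who belongs in the trial. Section 3.2 requires every inclusion criterion to be met, and section 3.3 says: "Participants who meet any of the exclusion criteria are not to be enrolled in this study". The hypothesis in section 2.1 concerns treatment-naïve patients without cirrhosis.

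The SAP lists per-protocol SVR12 among its secondary objectives, and Table 9 lists the per-protocol non-inferiority comparison as a secondary endpoint reported with the primary analysis.

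**The concern.** A per-protocol analysis normally asks whether the result holds among people who belonged in the trial and followed it. This set checks the second part and not the first. Someone with previous HCV treatment, fibrosis beyond F3 or a prohibited medication at entry counts as per protocol if they took the tablets and came back. Some of these features could affect SVR12: protocol Table 1 (section 5.3) notes that several listed medications may lower exposure to the study drugs.

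A reader of a non-inferiority trial looks at the per-protocol result beside the ITT result, because including people who do not belong can pull the arms together. As written, the per-protocol comparison does not remove that source of similarity. In addition, without a rule, any later decision to leave ineligible participants out would be taken in an open-label trial, possibly with outcomes known.

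**Working it through.** **Does another section supply the missing condition?**

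- Protocol section 10.5 defines ITT and mITT only, so there is no per-protocol definition to fall back on.
- The SAP's mITT and mITT-VF sets carry no eligibility condition.
- The sensitivity analysis in the SAP's Baseline Data section is triggered by large differences between arms at baseline, not by ineligibility.
- Protocol section 4.3 lists a significant protocol violation as a reason for which study drug may be discontinued, which would take that person out of the set. It is discretionary, and anyone who completes treatment stays in.

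None of these closes the gap.

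**The plan's own power figure.** Inputs (protocol section 10.1; SAP, Sample size and power): 125 standard, 250 simplified, SVR12 96% in both arms, margin 6 points, two-sided 95% interval.

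- SE = √(0.96×0.04/125 + 0.96×0.04/250) = 0.02147
- Power = Φ(0.06/0.02147 − 1.96) = Φ(0.835) = 79.8%

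This agrees with the stated figure of approximately 80%.

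**Effect of leaving ineligible participants in.** The documents give no number of violators, so a proportion f is assumed; 1% to 5% of 375 is about 4 to 19 people. Further assumptions: eligible participants are exactly at the margin (96% standard, 90% simplified), ineligible ones have 96% in both arms, and the per-protocol set is taken at 125 and 250.

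- Simplified-arm rate: p = 0.90(1 − f) + 0.96f
- True difference in the mixed set: −6(1 − f) points
- Chance of declaring non-inferiority: Φ[(0.06 − (0.96 − p))/SE − 1.96], with SE = √(0.96×0.04/125 + p(1 − p)/250)

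| f | p | Difference (points) | False non-inferiority |
|---|---|---|---|
| 0 | 90.00% | −6.00 | 2.5% |
| 1% | 90.06% | −5.94 | 2.6% |
| 2% | 90.12% | −5.88 | 2.8% |
| 5% | 90.30% | −5.70 | 3.3% |
| 10% | 90.60% | −5.40 | 4.2% |

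For f = 5%: SE = 0.02564, and Φ(0.0030/0.02564 − 1.96) = Φ(−1.843) = 3.3%.

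**Cost of removing them.** With the power formula above and 96% in both arms, removing the same share from each arm gives:

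| Removed | Per-protocol n | Power |
|---|---|---|
| none | 125/250 | 79.8% |
| 1% | 124/248 | 79.5% |
| 2% | 122/245 | 78.9% |
| 5% | 119/238 | 77.9% |
| 10% | 112/225 | 75.4% |

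These take all 375 as otherwise per protocol.

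**The case against.** The case for leaving the SAP alone has force. The set is explicit and reproducible, its definition contradicts nothing in the documents, and violations will be reported by number, type and reason. The per-protocol comparison is one of several secondary analyses; the primary conclusion rests on ITT, and nothing makes the per-protocol result a condition for claiming non-inferiority. All of that stands, and it limits the weight of the point. It does not answer why people barred by sections 3.2 and 3.3 should count as per protocol.

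Four stronger readings are tempting and are not supported.

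- **That ineligible participants bias the comparison toward one arm, or that their failures would be blamed on simplified monitoring.** Eligibility is settled before randomisation, so such participants are expected in both arms in the 1:2 ratio. Chance imbalance is possible; systematic favour is not implied. If they respond alike in both arms they shrink a real difference; if they respond differently by arm, the direction depends on how.
- **That about 5 and 10 failures should be expected in the per-protocol set.** Those counts are 4% of 125 and of 250, the ITT planning rate, where missing counts as failure. The per-protocol set drops discontinuations and non-attenders, so fewer failures are likely. If the rate were 98% (an assumption), the counts would be 2.5 and 5.
- **That one ineligible failure could readily change the conclusion.** An example can be built: 236/250 against 120/125 gives −1.60 − 1.96×2.277 = −6.06 points (not met), and dropping one simplified-arm failure, 236/249, gives −1.22 − 1.96×2.249 = −5.63 (met). But it is a selected boundary case. At 240/250 against 120/125 the bound is 0 − 1.96×2.147 = −4.21, and at 240/249 it is −3.76; the conclusion is the same. Summing binomial probabilities over all results where removing one simplified-arm failure turns not met into met gives about 5.5% at 96% in both arms and 0.8% at 98%, and even that presumes the removed failure was ineligible.
- **That every violation or exemption should be excluded.** Some criteria, such as albumin just below the lower limit of normal, have no evident link to SVR12, and an exemption may have been allowed deliberately.

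**Conclusion.** The gap is real: the SAP identifies people enrolled against the criteria and then lets them count as per protocol in a listed secondary non-inferiority comparison. Its expected consequence is modest. The false per-protocol non-inferiority rate moves from 2.5% to about 2.6% at 1% ineligible and 3.3% at 5%, on the assumptions that eligible participants are at the margin, that ineligible ones respond alike in both arms, and that the set is near its planned size. The effect matters only if ineligible enrolment is common, and its actual size cannot be known from the documents. The primary ITT analysis and the sample size of 375 are not in question. The reason to act is that the change is cheap and brings the set into line with the trial's own hypothesis.

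**What to change.** Add to the SAP's per-protocol definition that participants with a major eligibility violation are excluded. Prespecify the list, limited to criteria that could affect SVR12: for example previous HCV treatment, fibrosis stage beyond F3, or prohibited medication at entry. State whether participants granted an exemption stay in.

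Classify participants from screening and baseline data only, so that the extra visits in the standard arm cannot drive exclusions, and fix the classification before database lock without reference to HCV RNA outcome. Split Table 5 by arm. Leave ITT unchanged. If the sponsor prefers to keep these participants, the SAP should say so, give the reason, and add a sensitivity analysis without them.

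The cost is SAP wording, a slightly smaller per-protocol set and a slightly wider interval: about 2 points of power if 5% are removed. Trial conduct and sample size do not change.
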